# 2 Synopsis

Study Title	The Meso-ORIGINS Feasibility Study
Study Design	Multi-centre prospective feasibility study incorporating a retrospective multi-centre cohort study
Study Participants	Patients with Benign Asbestos Pleural Effusion (BAPE)
Sample Size	Prospective observational study: n = 54 (or n=27 feasible patients, whichever is reached first). Retrospective cohort study: n=300
Study Period	12 months
Sponsor	NHS Greater Glasgow & Clyde
Background and Rationale	MPM typically develops 30-50 years after inhalation of asbestos and is often presaged by radiological +/- clinical evidence of chronic pleural inflammation, and frequently by overt pleural effusion. The base agnostic pattern of DNA damage recently reported in MPM also suggests a prominent role for immune or inflammatory triggers. However, the recent genomic characterisation of MPM (1) poses major questions regarding the pressures that drive MPM evolution, being dominated by loss of tumour suppressors, with few protein-altering mutations in known oncogenes (1). Greater understanding of the driving (oncogenic) +/- permissive (immunological) events is required to design effective MPM treatments.
	In a future study called Meso-ORIGINS, we aim to define in vivo the key biological events that drive or permit evolution of MPM. Meso-ORIGINS will involve serial biological surveillance (using circulating markers, imaging +/- repeat pleural fluid and biopsies) over a 2-year period preceding the diagnosis of MPM. This will be achieved by recruitment of 850 patients with BAPE, of whom an estimated 12% (n=100) will develop MPM based on previous data (2). This will facilitate unprecedented surveillance of the key early biological events in MPM tumourigenesis.
	
 
The current feasibility study will address important areas of uncertainty regarding the current Meso-ORIGINS design, including:
 
within a prospective feasibility study, the technical feasibility and patient acceptability of a surveillance protocol including LAT, and alternative strategies limited to blood tests, imaging +/- pleural fluid sampling
 
within a retrospective cohort study, greater precision regarding the sample size estimate (currently n=850). This is based on a single study that reported a 2-year MPM transition rate of 12% (95%CI 4.5% - 26.4%) (2). If the true rate is close to the lower end of this 95% CI this may mandate an unfeasible sample size.
 

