### 4.5.2 Retrospective Cohort Study End-points

The **Primary End-Point** shall be the rate of MPM transition, defined as the number of eligible patients diagnosed with MPM within 2 years of the index diagnosis of BAPE divided by the total number of eligible patients.

The **Secondary End-Point** shall be a logistic regression model for MPM transition using baseline data as predictors.

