## 5.1 Scientific Background

#### 5.1.1 Introduction

MPM is an invasive thoracic malignancy associated with prior asbestos exposure. It typically develops 30-50 years after inhalation of asbestos fibres and frequently presents with breathlessness resulting from a pleural effusion. Median survival is poor at 9.5 months, and is principally determined by performance status and histological subtype. (10) Despite recent improvement in the resources available for the management of MPM, the disease remains universally fatal and there has only been a modest improvement in survival rates. (11)

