#### 5.1.3 Benign Asbestos-related Pleural Effusion

Patients with suspected pleural malignancy are frequently found to have non-specific pleuritis/pleural fibrosis at LAT or image guided biopsy. When associated with prior asbestos exposure, these patients are given the label of 'Benign Asbestos-related Pleural Effusion (BAPE)'. A retrospective, single-centre study of 142 LAT patients reported BAPE in 31% of patients, of whom12% (95% CI 4.5% - 26.4%) subsequently developed MPM over 2 years of follow-up (2). Consequently, patients with BAPE are routinely followed up in pleural clinics and repeat biopsies pursued if pleural effusion recurs or there are other indicators of MPM.

Benign asbestos-related pleural effusion (BAPE) is one cause of non-specific pleuritis. Although this syndrome was initially described in 1964 (18), the true nature and outcome of these patients has been poorly studied. In particular, it is not clear whether BAPE is a genuine precursor of MPM in some patients, or simply a reflection of false negative biopsies in a minority of patients with thoracoscopically occult MPM. Alternatively, BAPE could reflect an unrelated inflammatory episode that promotes MPM via the pro-angiogenic and immunosuppressive factors known to exist within pleural effusion (19). Whatever the mechanism, BAPE constitutes a unique cohort in which to study early MPM biology.

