#### 6.2 Exclusion Criteria

All study participants involved in either the Prospective Feasibility Study or the Retrospective Cohort Study will be subject to the following exclusion criteria:

- Histological diagnosis of MPM or any secondary pleural malignancy
- Diagnosis of pleural infection, empyema or granulomatous pleuritis

In addition, potential cases identified for the Retrospective Cohort Study must also be assessed against the following **additional exclusion criterion:** 

• < 2 years follow-up completed at the point of enrolment

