### 6.4 Retrospective Cohort Study Case Identification

Electronic databases will be used to identify cases meeting the study eligibility criteria. Existing databases in the trial centres involved contain data on approx. 1000 patients that have undergone LAT. These database should contain approx. 300 cases of BAPE based on previously published BAPE incidence of 30% in this population (2). Existing databases from VATS and image guided biopsy cases will also be used.

Cases can be entered throughout the period that the study is open. This includes cases diagnosed with BAPE with less than 2 years follow-up at the point the study opens, so long as 2 years follow-up has concluded by the time they are enrolled. The retrospective study will end after 12 months from opening and therefore patients who had a diagnosis of BAPE following LAT on or before 31/11/17 could be recruited.

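### The retrospective criterion of 2 years' completed follow-up can be applied so that early deaths, including MPM cases, are excluded, which would bias the 2-year transition rate

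*Protocol*

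**What the plan says.** Section 6.2 of the protocol gives the additional retrospective exclusion as "< 2 years follow-up completed at the point of enrolment". The synopsis states the same rule both as an inclusion and as an exclusion criterion. Sections 6.4 and 8 allow recent cases to be entered "so long as 2 years follow-up has concluded by the time they are enrolled". Section 6.1 carries no follow-up criterion.

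Section 4.5.2 sets the numerator of the primary end-point: "the number of eligible patients diagnosed with MPM within 2 years of the index diagnosis of BAPE". For the denominator, the same sentence says that this count is "divided by the total number of eligible patients". Section 10.2.2 repeats the definition.

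Section 6.4 also derives a calendar consequence of the rule: "patients who had a diagnosis of BAPE following LAT on or before 31/11/17 could be recruited".

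Section 5.1.1 says of MPM: "Median survival is poor at 9.5 months".

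The follow-up part of the section 8 form asks for any new pleural diagnosis and whether MPM was diagnosed within 2 years of the index procedure. Elsewhere section 8 records the date of BAPE diagnosis and of the index procedure. It lists no date of MPM diagnosis, death or last contact.

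**The concern.** Whether a patient has completed 2 years of follow-up is known only after the index diagnosis, and it is related to the outcome. Take a patient diagnosed with MPM at month 6 who dies at month 15. The event happened inside the window, but the patient never completed 2 years of follow-up. Read literally, the rule removes that patient from numerator and denominator. A site might instead keep such a patient because the end-point was reached, yet drop a patient who died of something else at month 15. The error then runs the other way.

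The retrospective cohort exists to estimate this one rate more precisely, and the rate sets the size of Meso-ORIGINS. The synopsis and section 5.2 say that a low rate may make that study unfeasible. A selection rule that can produce a low or a high rate by itself undermines that purpose, and enlarging the cohort to 300 does not reduce this kind of error.

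**Working it through.** **The plan's own figures.**
- The prior rate is 12% with 95% CI 4.5% to 26.4% (synopsis; section 5.1.3). The documents give no counts. A Wilson interval with continuity correction for 5/42 gives 11.9% (4.47% to 26.43%), which matches, so 5/42 is inferred. Section 5.1.3 implies about 142 × 0.31 = 44 BAPE patients.
- Meso-ORIGINS: 850 × 0.12 = 102, stated as about 100 MPM cases.
- Retrospective target: 1000 × 0.30 = 300 (sections 6.4 and 10.1.2).

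These figures are not in dispute.

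**Model for the literal reading.**
- p = 0.12, the true 2-year rate, so 36 of 300 patients develop MPM and 264 do not.
- s = share of MPM cases still alive 24 months after the BAPE diagnosis.
- d = 2-year mortality without MPM. The documents do not give it; 5-30% is assumed.
- Survival after MPM diagnosis is taken as exponential with the protocol's 9.5-month median: k = ln 2 / 9.5 = 0.0730 per month.
- MPM diagnoses are assumed evenly spread over 0-24 months.

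s = (1 − e^(−24k)) / (24k) = (1 − 0.174) / 1.751 = 0.472.

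MPM cases kept: 36 × 0.472 = 17.0, so about 19 of 36 are lost. The observed rate is 17.0 / (17.0 + 264(1 − d)), and the number needed for 100 MPM cases is 100 / rate.

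| d | Patients kept | Observed rate | n for 100 MPM cases |
|---|---|---|---|
| 5% | 267.8 | 6.3% | about 1,580 |
| 15% | 241.4 | 7.0% | about 1,420 |
| 30% | 201.8 | 8.4% | about 1,190 |

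**If sites keep MPM cases but drop other deaths.** The rate is 36 / (36 + 264(1 − d)).

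| d | Observed rate | n for 100 MPM cases |
|---|---|---|
| 5% | 12.6% | about 800 |
| 15% | 13.8% | about 720 |
| 30% | 16.3% | about 610 |

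**If everyone with an index diagnosis at least 2 years earlier is kept.** The rate is 36/300 = 12%, with exact 95% CI 8.5% to 16.2%. All three literal-reading rates in the first table fall below that interval.

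**Sensitivity of the literal reading to MPM timing (d from 0 to 40%).**

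| MPM diagnosed | s | Observed rate |
|---|---|---|
| all at 6 months | 0.27 | 3.5% to 5.8% |
| all at 12 months | 0.42 | 5.4% to 8.7% |
| evenly spread | 0.47 | 6.0% to 9.7% |
| all at 18 months | 0.65 | 8.1% to 12.8% |

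Algebraically, the observed rate is below p whenever d < 1 − s. That threshold is about 53% for even spread and about 35% if all diagnoses come at 18 months. Above it, the bias is upward.

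**The case against.** The strongest reply is that calendar time was meant. Section 6.4 turns the rule into a cut-off on the date of diagnosis alone, with no condition on being alive. The count of 300 points the same way: 1000 × 30% is carried straight to the target with nothing deducted for deaths, whereas the literal rule would leave about 241 of 300 at d = 15%. Section 6.2 also excludes a histological diagnosis of MPM without naming a time point. That must mean at index, or every histologically confirmed transition would be excluded, so a purposive reading of its neighbour is fair. On the calendar reading deaths are kept and this bias disappears.

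This stands as evidence of intent, but it does not settle how the rule will be applied. The cut-off sentence says who could be recruited, not that those who died are included. The count is not decisive, because VATS and image-guided biopsy databases are used as well. The operative criterion speaks of completed follow-up, and several centres extract the data.

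Two stronger inferences are tempting. One is that the missing dates make any error irreparable. The documents do not support this: the data are linked to study IDs and come from databases and health records, so sites could go back to source. The other is that early death of MPM cases is established as the usual course in this cohort. The 9.5-month median describes MPM in general, and the 53% loss depends on assumed timing.

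**Conclusion.** The criterion is ambiguous on a point that determines the retrospective primary end-point. Followed literally, it conditions the 2-year rate on surviving and being followed for 2 years. For a true 12%, the observed rate would be 6.3-8.4%, or 12.6-16.3% if MPM cases are kept and other deaths dropped. The corresponding Meso-ORIGINS sizes are about 1,190-1,580 and 610-800, against the planned 850.

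These sizes rest on even timing of MPM diagnosis, exponential survival with the protocol's median, and assumed non-MPM mortality of 5-30%. Other timings widen the range and can reverse the direction.

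A reader might conclude that the rate will be biased, and biased downward. The documents do not support that: the cut-off in section 6.4 allows a reading with no bias from deaths. What they do support is that the wording permits the bias, does not rule it out, and may be applied differently between centres.

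**What to change.** In the synopsis, section 6.2, section 6.4 and section 8, replace the follow-up criterion with: *index BAPE pathology report dated at least 24 months before enrolment, regardless of death, MPM diagnosis or loss to follow-up within that time*. State that MPM diagnosed before death counts as an event. Section 6.1 needs no change.

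Add the dates of MPM diagnosis, death and last contact to the section 8 form, so that incomplete follow-up can be identified. A cumulative incidence of MPM with death as a competing event could be reported beside the simple proportion. That is optional, and the eligibility change does not depend on it.

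The cost is a wording change in four places, three date fields and a little more data extraction. No extra patients are needed.

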# 6.3 Prospective Feasibility Study Screening and Recruitment

Patients potentially meeting the eligibility criteria will be identified at routine outpatient clinics, lung or pleural MDTs and/or during inpatient reviews or LAT sessions. A medically qualified investigator will review inclusion and exclusion criteria and complete the eligibility assessment form. Patients that meet all inclusion criteria and who do not have obvious exclusion criteria will be recorded in a screening log. Eligible patients will be provided with a Patient Information Sheet (PIS) and invited to participate on a consecutive basis. This activity will occur at routine outpatient clinic. All patients will be given sufficient time to consider study participation (in their own judgment); this need not be 24 hours or greater.

If patients are agreeable to trial involvement, a member of the research team will identify a suitable opportunity to address any questions and to seek written informed consent prior to study enrolment. Provision of the study PIS, study discussion, consent and enrolment can all occur on the first study visit (see Section 7).

### 6.4 Retrospective Cohort Study Case Identification

Electronic databases will be used to identify cases meeting the study eligibility criteria. Existing databases in the trial centres involved contain data on approx. 1000 patients that have undergone LAT. These database should contain approx. 300 cases of BAPE based on previously published BAPE incidence of 30% in this population (2). Existing databases from VATS and image guided biopsy cases will also be used.

Cases can be entered throughout the period that the study is open. This includes cases diagnosed with BAPE with less than 2 years follow-up at the point the study opens, so long as 2 years follow-up has concluded by the time they are enrolled. The retrospective study will end after 12 months from opening and therefore patients who had a diagnosis of BAPE following LAT on or before 31/11/17 could be recruited.

#### 6.5 **Co-enrolment Guidelines**

There will be no restriction on co-enrolment in other studies. However, the lead centre must be informed of such activity as soon as possible.

#### 6.6 Bias Reduction

In the retrospective study there is potential for recall and omission bias in data collection. We expect that this will be minimal as each centre that will be collecting data will have prospective databases where all LAT/VATS/image guided biopsies are recorded. In the prospective feasibility study there will be consecutive multicentre recruitment which will improve generalisation to a UK population. This is important as the data gathered will ultimately be used in the design of a future larger study.

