# 8 Retrospective Study Data Collection and Recording

The following data will be recorded retrospectively for all eligible patients using LAT/VAT/image guided biopsy databases and electronic health records at the study centres. A data collection form (.x/s) will be provided, including pre-populated study IDs. All data will be recorded in a linked anonymised format.

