# The date of BAPE diagnosis will be recorded. This is defined as the date on the pathology report describing features of BAPE that meet they eligibility criteria as explained in section 6.

Imaging, pleural fluid and blood results should be recorded at first presentation.

Cases can be entered throughout the period that the study is open. This includes cases diagnosed with BAPE with less than 2 years follow-up at the point the study opens, so long as 2 years follow-up has concluded by the time they are enrolled.

Demographics	Age*, Gender
Asbestos Exposure History	Occupational or environmental Nature of Occupation
CT Findings*	
 
Benign or Malignant Features
 
Based on previously reported criteria (5,11)
 
Calcified Pleural plaques
 
Present or Not Present
 

CXR appearance*	Effusion Laterality Effusion Size: • Small effusion (<50% thorax) • Large effusion (≥50% thorax)
Blood Tests*	Haemoglobin Neutrophils Lymphocytes Platelets CRP Albumin LDH Total Protein

Pleural Fluid	Total protein Albumin LDH Glucose Colour Cytology
LAT/VATS Findings	Date index procedure performed Were adequate views obtained? Which surfaces were abnormal? What was the nature of the abnormality/ies? • Smooth • Macro-nodular • Micro-nodular Number of biopsies Did the lung prove non-expansile (based on BTS criteria (≥50% re-apposition) (20) Did the subject have pleurodesis? Did the subject have an IPC placed? Histology, Cytology, Pleural Fluid Chemistry Results
Follow-up Data	Record any new pleural diagnosis since LAT/VATS Record whether MPM diagnoses within 2 years of index LAT/VATS date

\*at presentation

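### In the retrospective cohort, CT features are recorded after the MPM outcome is known and on the same form; section 6.6 does not address this, so predictor effects may be inflated

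*Protocol*

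**What the plan says.** Protocol section 6.2 excludes from the retrospective cohort anyone with "< 2 years follow-up completed at the point of enrolment". Sections 6.4 and 8 repeat that 2 years must have elapsed before a case is entered.

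Section 8 has sites complete a spreadsheet for each eligible patient "using LAT/VAT/image guided biopsy databases and electronic health records at the study centres". Its baseline items include CT findings, classed as "Benign or Malignant Features" against published criteria cited as references 5 and 11. For LAT/VATS it asks "What was the nature of the abnormality/ies", with smooth, macro-nodular and micro-nodular as options. The same form ends with the outcome: "Record whether MPM diagnoses within 2 years of index LAT/VATS date". Imaging values are to be those at first presentation.

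Section 6.6 names recall and omission as the possible biases of the retrospective study. It judges them small: "We expect that this will be minimal as each centre that will be collecting data will have prospective databases". The databases it refers to hold LAT, VATS and image-guided biopsy procedures.

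Sections 4.5.2 and 10.2.2 make a logistic regression for MPM transition, with baseline data as candidate predictors, the secondary end-point. Section 4.5.1 gives its purpose as refining Meso-ORIGINS eligibility.

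**The concern.** Whenever the form is filled in, the 2-year outcome already exists in the records being searched. The Protocol does not say who completes the form, in what order, whether the CT item is copied from the original report or judged afresh, or whether the recorder is unaware of the outcome. A recorder who knows that a patient developed MPM may lean towards calling an equivocal scan malignant. That error depends on the outcome, so it pushes the association away from the null.

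Two features of the text leave room for it. Section 5.1.2 reports that almost half of patients with an eventual diagnosis of pleural malignancy have a benign CT, so many MPM cases could have scans open to hindsight. And the criteria are not clearly identified: references 5 and 11 are, in the reference list, an exhaled-breath study and a survival-prediction study. Section 7.4.1 cites 9 and 15 for the same item, and section 5.1.2 cites 13 and 14 for CT features of malignancy.

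At stake is whether a CT or pleural-appearance criterion enters the eligibility rules of a planned study of about 850 patients on the strength of an association partly created by the way the data were recorded.

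**Working it through.** **Inputs from the Protocol**
- Target sample size 300 (section 10.1.2), from about 1000 LAT patients and 30% BAPE: 1000 × 0.30 = 300. This reproduces.
- Transition rate 12%, 95% CI 4.5% to 26.4% (Synopsis; section 5.1.3). Expected MPM cases: 300 × 0.12 = 36, leaving 264 non-cases. Over the interval: 300 × 0.045 = 13.5 and 300 × 0.264 = 79.2, so about 14 to 79.

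**Assumptions (not in the Protocol)**
- Feature prevalence p: 30%, with 20% and 50% as a range.
- Share f of truly benign CTs in MPM patients recorded as malignant because the outcome is known: 5%, 10%, 20%.
- One unadjusted two-by-two table tested at two-sided 0.05. The Protocol states no threshold for the predictor model.

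**Formulas.** With no true effect, the recorded prevalence in MPM cases is p₁ = p + f(1 − p), and the odds ratio is [p₁/(1 − p₁)] / [p/(1 − p)].

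**Results at p = 0.30** (reference odds 0.30/0.70 = 0.429; 36 cases against 264)

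| f | p₁ | Odds in cases | Odds ratio | Chance of p<0.05 | Patients recoded, 36 × 0.70 × f |
|---|---|---|---|---|---|
| 5% | 0.335 | 0.504 | 1.18 | about 7% | 1.3 |
| 10% | 0.370 | 0.587 | 1.37 | about 14% | 2.5 |
| 20% | 0.440 | 0.786 | 1.83 | about 40% | 5.0 |

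With f = 0 the odds ratio is 1.0 and the simulated rejection rate about 4%.

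**Sensitivity**
- Prevalence from 50% down to 20%, 36 cases: 10% recoding gives an odds ratio of 1.22 to 1.56 and p<0.05 in about 8% to 22%; 20% recoding gives 1.50 to 2.25 and about 20% to 58%.
- Events from 14 to 79, prevalence 30%: 20% recoding gives p<0.05 in about 20% to 61%. With 14 events and 10% recoding it is about 8%.
- Smaller recoding: at 2%, the odds ratio is 1.07 and the rejection rate about 5%.
- A true odds ratio of 2.0 at 30% prevalence would appear as 2.23, 2.48 or 3.08 with 5%, 10% or 20% recoding.
- Error unrelated to outcome works the other way. With assumed sensitivity 0.8 and specificity 0.9, non-cases show 0.8 × 0.30 + 0.1 × 0.70 = 0.310. Cases, with true prevalence 0.462 at an odds ratio of 2.0, show 0.8 × 0.462 + 0.1 × 0.538 = 0.423. The observed odds ratio is (0.423/0.577)/(0.310/0.690) = 1.63.

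**What section 6.6 covers**
- *Cases omitted from the cohort:* yes, if every procedure is logged prospectively.
- *LAT/VATS appearance:* partly, if appearance was entered at the procedure. The Protocol does not say so.
- *CT classification:* no. CT is not among the contents named.
- *Knowledge of the outcome while recording:* not mentioned.

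**The case against.** The best counter-argument is that the text speaks of data being recorded, not graded. Results at first presentation may simply be copied from reports issued at the time. No image retrieval, re-reading or reader is specified for this cohort, and the data form itself is not shown. This stands as far as it goes: a reader might infer that scans will be re-graded two years later, but the Protocol does not say that. It is silent, and asking for a classification against published criteria does not rule re-grading out. Fixing the reference time at first presentation determines which scan counts, not when or by whom it is classified.

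Second, thoracoscopic appearance may already be protected, because section 8 uses the procedure databases as a source of data items and not only to find cases. That also stands in part, so the gap is clearest for CT.

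Third, a reader might conclude that predictor effects will be inflated. The documents do not support that. Inflation requires coding driven by the outcome; ordinary transcription error would weaken associations instead.

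Fourth, the illustrated sizes rest on assumed prevalence and recoding shares, and at 2% to 5% recoding they are small. This is correct, and the figures should be read as a range of possibilities.

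Finally, abstraction instructions might sit in a document not shown. But section 6.6 is the Protocol's own bias statement and section 8 its definition of data capture, and an analysis plan cannot repair a predictor already coded with the outcome in view.

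**Conclusion.** The point holds as a gap in bias control for the retrospective secondary end-point. CT classification, and LAT/VATS appearance unless entered at the procedure, is recorded after the outcome is known and on the form that holds the outcome. The ground given in section 6.6 does not reach CT classification. Effects of these predictors may be inflated, by an amount the documents cannot determine. Under the stated assumptions, moving one to five patients takes a null odds ratio to between about 1.18 and 1.83.

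The retrospective primary end-point, the transition rate, and the prospective feasibility end-point do not use these predictors and are unaffected. The change is worth making because it is nearly free and the model is meant to shape eligibility for the main study; the study does not fail without it.

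**What to change.** In section 8:
- Require CT features to be taken from the report issued at the time, dated on or before the index pathology report, and LAT/VATS appearance from the procedure record made at the time. Allow no re-reading, and add a 'not stated' option.
- Require the baseline columns to be completed before the follow-up columns.
- Correct the citation to references 5 and 11 so that it identifies the CT criteria intended, and reconcile it with section 7.4.1.

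In section 6.6, limit the statement that bias is minimal to omission of cases, and name outcome-aware recording of predictors as a residual bias.

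The cost is wording in two sections and on the data form, with no additional reader. Some values will be 'not stated', in a number that cannot be predicted from the Protocol. Column order reduces awareness of the outcome but does not remove it among staff who know the patient, so the main protection is the restriction to contemporaneous sources.
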